D.1.1 Overview and Design. The proposed pilot study is designed as a culture-directed versus empiric antibiotic strategy for patient-reported UTI symptoms in older women. (Figure 2) Over 12 months, we will recruit 70 women with rUTI. Following enrollment, patients will be randomized in a 1:1 ratio to one of two groups. Patients assigned to the culture-directed arm will await results of urine culture prior to potentially receiving antibiotics and those assigned to the empiric arm will be prescribed immediate antibiotics from an established list of commonly prescribed antibiotics. Participants will be sent electronic questionnaires after urine culture results and then weekly for a total of 4 weeks. The primary outcome is feasibility of trial defined as recruitment of 10% of eligible participants with 70% adherence to study protocol.

D.1.2 Recruitment and Subject Eligibility. Women age ≥65 years⁶¹ with diagnosis of recurrent UTI (rUTI) will be recruited from: 1) UPMC WCBPH faculty practices or 2) CTSI Pitt+Me® Research Registry. Eligibility criteria are listed in Table 2.

Rationale for Inclusion Criteria: We will include participants with patient reported recurrent UTI to allow for a pragmatic study design and generalizability. Additionally, our definition of patient reported UTI is like other RCTs evaluating non-antibiotic options as compared to antibiotic strategies for UTI treatment.^{43,62} We will exclude participants with features of complicated UTI in the setting of structural or functional abnormalities or instrumentation /catheterization^{4,63} Eligibility is limited to female biologic sex given the differential risk profile of males and females who experience recurrent UTIs.

D.1.3 Study procedures (Figure 2).

D.1.3.1 – Screening and Enrollment Procedures.

Information on the REDUCTION trial will be broadly disseminated in the University of Pittsburgh faculty practices at the WCBPH, through IRB approved brochures, social media ads, institutional (MWRI) and CTSI websites. Interested women will be encouraged to contact the research staff for more information. Women who meet eligibility criteria after screening will be provided a consent form via their preferred method (electronic or paper).

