
Pelvic floor distress inventory, PFDI-20; Urinary Tract Infection Symptom Assessment, UTISA
 * Adverse events will include either antibiotic related side effects, signs/symptoms of pyelonephritis and/or urosepsis or other serious adverse events

D.1.7. Data analysis.

Specific aim 1A) To evaluate the feasibility of recruiting eligible participants into a randomized trial of a culture-directed versus empiric antibiotic strategy for patient-reported UTI symptoms in older women.
 All outcomes for the feasibility assessment will be descriptive using numbers and proportions of patients and 95% CIs. We will report the number of patients assessed for eligibility along with the numbers excluded based on not meeting inclusion criteria, participation declined, and other reasons.⁷⁴ We will document number and proportion of enrolled participants who were randomized along with the number/proportion who received their

allocated assignment. We will document those lost-to follow-up including potential reasons. These data will provide information on the feasibility of recruiting patients into a future, large randomized, placebo controlled clinical trial. We believe that successfully recruiting 10% of eligible patients (e.g., 6-7 patients per month) will confirm the capacity to recruit for a future trial.

Power calculation:^{75,76} The primary outcome is feasibility which we will define as the ability to recruit 10% of eligible patients. As this is a pilot study, the sample size of 70 patients was determined based on clinical and logistical resources rather than statistical requirements for hypothesis testing. We anticipate screening approximately 1200 potentially eligible patients (based on known clinical data from our practice and current enrollment of women with recurrent UTI in Pitt+Me®) during the 12 months of recruitment (~100 per month) of which at least 800 will be deemed eligible and have UTI symptoms. (~67 per month) This is based on data from our group on urine cultures sent annually and time between UTI episodes.³⁵ A 95% confidence interval (CI) for the recruitment rate provides a 2.4% margin of error (MoE) assuming the true rate is 10%.

Specific aim 1B) To evaluate participant adherence to study procedures.

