Analysis. All outcomes will be described using numbers and proportions of patients or means with confidence intervals. Proportions between groups will be compared with either chi-square or Fischer's exact testing and means will be compared with student's t-testing. Exploratory logistic regression modeling will be utilized to investigate the odds of both initial treatment failure and/or recurrent of UTI symptoms between groups and based on baseline characteristics

Power analysis:^{76,79} As above, we propose a future trial with a primary outcome to be symptom resolution at day 14 defined as 2 or less points (slight, very slight, or no problems) on all five components of the UTI symptom assessment (UTISA).^{43,78} The literature suggests 58-80% of women receiving empiric antibiotics for patient reported UTI will achieve clinical cure by day 3-7 after treatment initiation.^{43,78} Given that only women

with a positive urine culture will be given culture-directed antibiotics, and women in the empiric arm may have to have their antibiotics changed or stopped at the time of culture result, we anticipate a higher proportion of those in the culture-directed arm to have symptom resolution at day 7. Assuming 70% symptom resolution in the empiric arm, a future trial of 262 participants, with 131 per arm, would have 80% power to detect a 15-percentage point difference between groups with a 2-sided alpha of 0.05, while a sample size of 300 would be required assuming 65% resolution. Therefore, we believe that successfully recruiting a total of 70 participants at a rate of 6-7 participants/month will confirm the feasibility of future trial completion in <4 years (equivalent to other trials of antibiotic regimens for symptomatic UTI).^{17,78}

Statistical methods

Primary Outcomes	Statistical analysis
Feasibility: 
 - Number of subjects that were screened for participation - Number and proportion of subjects screened who met inclusion/exclusion criteria - Number and proportion of subjects who either declined participation or were ineligible (including reasons for ineligibility) - Number and proportion of eligible subjects that were enrolled in the study - Number and proportion of subjects enrolled who completed the study - Monthly enrollment rate 	Descriptive analysis = counts and proportions or means with standard deviation

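### The 10% recruitment criterion is tied to a forecast of about 800 eligible women, but the described screening route is women making contact, and nothing says who is logged as eligible

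*Combined protocol and SAP*

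**What the plan says.** D.1.1 sets the criterion: "The primary outcome is feasibility of trial defined as recruitment of 10% of eligible participants with 70% adherence to study protocol". The power calculation in D.1.7 repeats the recruitment part: "The primary outcome is feasibility which we will define as the ability to recruit 10% of eligible patients".

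The size of the eligible pool is also in D.1.7: "We anticipate screening approximately 1200 potentially eligible patients", a figure "based on known clinical data from our practice and current enrollment of women with recurrent UTI in Pitt+Me". At least 800 of these are expected to be eligible and symptomatic, about 67 per month, from the group's data on urine cultures sent each year and the interval between episodes. Under Specific aim 1A, recruiting 10% of the eligible is illustrated as 6-7 women per month.

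On entry to the study, D.1.2 says women "will be recruited from: 1) UPMC WCBPH faculty practices or 2) CTSI Pitt+Me® Research Registry". D.1.3.1 then describes brochures, social media advertisements and websites, followed by: "Interested women will be encouraged to contact the research staff for more information". Women found eligible at screening are given a consent form, and D.1.3.2 schedules interested women for a baseline visit once symptoms develop.

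On reporting, Specific aim 1A promises "We will report the number of patients assessed for eligibility", with counts of exclusions and refusals. The Statistical methods table lists "Number and proportion of eligible subjects that were enrolled in the study" and the monthly enrollment rate.

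**The concern.** A recruitment percentage means something only relative to its denominator. The threshold was set against a population forecast: symptomatic women in the practices and registry, whether or not they had heard of the trial. The written procedure yields a different group, namely women who saw the material and got in touch. Enrolled over eligible among those women measures conversion of enquiries, and it will usually be higher than uptake in the population.

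The plan does not say which group is counted. It also leaves open when a woman becomes eligible. D.1.3.1 has eligibility established before the consent form is given. D.1.3.2 has it settled finally at the baseline visit, in a step listed after consent is signed. It is also unclear whether a woman who passes screening but has no symptomatic episode stays in the denominator.

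At stake is the recruitment half of the primary outcome. The rule could be met or missed because of how the log is kept, and a pass on a small log would say little about reaching the accrual the larger trial needs. The adherence half is not affected.

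**Working it through.** **Inputs.** From D.1.1: 70 women in 12 months and the 10% threshold. From D.1.7: about 1200 screened, at least 800 eligible with symptoms, 6-7 recruits per month, and a 2.4% margin of error at a true rate of 10%. From the power analysis for the future trial: 262 participants in under 4 years. The documents give no eligible count other than 800, so every other log size below is an assumption.

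**Step 1: which denominator the threshold is tied to.** 800/12 = 66.7 eligible per month, and 10% of that is 6.67 per month. This reproduces the plan's 6-7. Conversely, 6-7 per month is 72-84 per year, which is 10% of 720-840 women. So 10% and 6-7 per month are the same test only when about 720 to 840 women are logged as eligible.

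**Step 2: what happens with a different log.** Rate = enrolled / logged eligible; accrual needed to reach 10% = 0.10 × logged / 12.

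| Logged eligible | Needed for 10% | Per month | Rate with 20 enrolled | Rate with 70 enrolled |
|---|---|---|---|---|
| 200 (assumed) | 20 | 1.67 | 10.0% | 35.0% |
| 400 (assumed) | 40 | 3.33 | 5.0% | 17.5% |
| 700 (assumed) | 70 | 5.83 | 2.9% | 10.0% |
| 800 (plan's forecast) | 80 | 6.67 | 2.5% | 8.75% |

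The telling case is 20 enrolled. Against 200 logged, the rule is met at 20/12 = 1.7 per month; against 800, it is missed by a wide margin. At 20 per year, the 262-participant trial would take 262/20 = 13.1 years.

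**Step 3: the plan's own figures against 800.**
- Target: 10% × 800 = 80, but the target is 70, and 70/800 = 8.75% (Wilson 95% CI 7.0% to 10.9%). Full accrual against the forecast pool gives a point estimate below the threshold. The figure of 70 is 10% of 700.
- Margin of error: 1.96 × √(0.10 × 0.90 / 800) = 2.08%. Wilson also gives 2.08%; Clopper-Pearson and the continuity-corrected Wald interval give 2.14%. The stated 2.4% needs n = 0.09 × (1.96/0.024)² ≈ 600 (576 to 626 allowing for rounding). It is not reproduced at 800, nor at 1200 (1.70%).

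The monthly figure therefore points to 800 eligible, the target to 700 and the precision to about 600.

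**The case against.** The strongest reply is that the plan does not restrict screening to women who call. D.1.2 names the practices and the registry as sources, B.7 describes Pitt+Me as matching registry participants algorithmically from diagnoses and demographics, and D.1.7 expects about 1200 to be screened. The study flow diagram (Figure 2) is not available in the text reviewed and may show more. This stands in part: a reader might infer that self-referral is the only route, and the documents do not support that. They are silent on active identification in the procedure and on whether matched women who never respond are counted.

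A reader might also infer that the log would contain only women who already want to join. That goes too far: women make contact to learn more, and the plan will count those who decline.

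Nor does the percentage stand alone. The 6-7 per month figure, the target of 70 and the reported monthly enrollment rate do not depend on the log, so weak accrual behind a small denominator would be visible. This tempers any claim that capacity for the larger trial would necessarily be overstated. It does not remove the problem, because the defined primary outcome is the proportion and 6-7 per month is given as an illustration of it.

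Finally, 8.75% at full accrual might be read as an effect of the screening route. It is not. It would arise with a perfect log, because the target of 70 is below 10% of 800. Likewise, the 2.4% margin of error cannot be cited as resting on 800.

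**Conclusion.** The point holds as a gap in the definition of the primary outcome. The recruitment threshold is calibrated to about 800 eligible symptomatic women, the one screening procedure described begins with women making contact, and no section fixes who is logged as eligible. If the log consists mainly of women who make contact, the rate is inflated relative to the threshold. In the assumed example of 20 enrolled, it is 10% of 200 but 2.5% of 800, a factor of four, at 1.7 per month against an intended 6-7. How far this would occur in practice cannot be determined, because the log size is an assumption and active identification may be planned. Separately, the target of 70 and the 2.4% margin of error do not match 800 and need reconciling whichever denominator is chosen. The matter should be settled before recruitment.

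**What to change.** State before recruitment that the 10% rule is assessed on the following basis.

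- **Denominator:** women in the WCBPH practices and Pitt+Me who meet those Table 2 criteria that can be checked in records and have a symptomatic episode during the 12 months. Each woman is counted once, whether or not she contacts staff, using the same data as the 1200/800 forecast.
- **Numerator:** enrolled women from those same two sources.
- **Reported separately:** the rate among women actually screened, and the women who came only through advertisements.
- **Interpretation:** read the percentage together with the 6-7 per month accrual criterion.
- **Figures:** restate them on this denominator. If 800 stands, 10% is 80 women and the margin of error is about 2.1%. The target of 70 (8.75% of 800) and the threshold must be brought into line with each other.

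The cost is protocol wording and a periodic query of data the team has already used. There are real drawbacks. Patient-reported criteria, such as infection history, symptoms and willingness to comply, cannot be confirmed for women never contacted, so the denominator is approximate. The rate will measure reach as well as willingness, and it will be lower than one computed among enquirers; reporting the rate among screened women alongside it helps separate the two.

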- This visit will first take place with a research coordinator where the participant will be allowed to ask any final questions about their consent which will then be signed either on paper or electronically.
- Final eligibility will be determined by a licensed medical provider on the research team by ensuring the participant is not experiencing any symptoms of pyelonephritis and/or sepsis.
- Consented study participants will then complete baseline questionnaires including the Urinary Tract Infection Symptom Assessment (UTISA)⁶⁸ and the pelvic floor distress inventory short form (PFDI-20).⁶⁹
- Participants will submit a urine specimen for urine culture and urinalysis either in-person at one of our Women's Center for Bladder and Pelvic Health faculty practices or a local laboratory

Randomization: Participants will be randomized by the study team to either the “Culture-directed Antibiotic Treatment” or “Empiric (Immediate) Antibiotic Treatment” Group in a 1:1 allocation scheme, with randomization using permuted blocks of 4 or 6.

D.1.3.3 Antibiotic Treatment Strategy. All participants will be allowed to use acetaminophen, non-steriodals, and/or phenazopyridine.

Culture-directed Antibiotic Treatment: Participants will be directed to refrain from taking antibiotics until results of urine culture are reported, which is expected within 48-72h.

Empiric Antibiotic Treatment Participants will be prescribed empiric antibiotics in accordance with our stepwise protocol below.

Antibiotic Protocol. For participants in the empiric Rx arm, we will choose an antibiotic with consideration of patient reported allergies, current medications and current IDSA guidelines.⁷⁰ If there is a contraindication to the first antibiotic on the list they will progress to the next option until a suitable selection is achieved.

Antibiotic Protocol:

1. Nitrofurantoin 100 mg PO BID x 5 days
2. Trimethoprim/Sulfamethoxazole 875/125 mg PO BID x 5 days
3. Fosfomycin 3 g once
4. Cephalexin 500 QID x 5 days
5. Ciprofloxacin 500 mg PO BID x 5 days

D.1.3.4 Antibiotic management after urine culture results. All participants will be called with the results of their culture. Participants who register for *MyUPMC*, a no-cost, proprietary secure email service, will also receive the urine culture result by email. Cultures with result of “mixed flora” will be considered contaminated and be managed as negative.⁷¹

Culture-directed Antibiotic Treatment.

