- Those with a negative urine culture will not be prescribed antibiotics and will be followed per protocol.
- Those with a positive urine culture who *report persistent UTI symptoms* will be given antibiotics following the priority list above with consideration to reported antimicrobial sensitivities.
- Those with a positive urine culture who *report resolution of UTI symptoms* will not be given antibiotic

Empiric Antibiotic Treatment.

- Those with a negative urine culture will be told to stop antibiotics
- Those with a positive urine culture sensitive to the empiric antibiotic will be instructed to complete the full course of their antibiotics
- Those with a positive culture resistant to empiric antibiotic will be given an alternative antibiotic per antibiotic protocol and will be followed per protocol. If there are no oral antibiotic options with patient-specific and antimicrobial sensitivities, we will engage local infectious disease physicians for management as per standard clinical protocols.

[figure not shown]
D.1.6. Study follow-up assessments.

All participants will be followed with electronic surveys via Research Electronic Data Capture (REDCap) software, which is a browser-based, metadata-directed EDC software and workflow methodology for designing

clinical and translational research databases,⁷² on day 2-3 (after result of urine culture). To avoid limiting enrollment to only those with access to technology, our research coordinator can also call and administer the questionnaire by phone to ensure ability to access and complete electronic materials. Follow-up assessments will be completed weekly for a total of 4 weeks. These will include UTISA questionnaire,⁶⁸ antibiotic associated side effects, use of other symptom mitigating remedies, and adherence to assigned study arm.

Participants will be provided with a clinical line to call 24/7 with report of worsening symptoms which will be discussed with the PI, [name] for determination of antibiotic prescription and if participants report fevers or chills this will prompt an in-person evaluation in clinic during business hours or the emergency department after hours. If participants call to report new symptoms during the study course, a repeat urine culture will be obtained.⁷³ Given that these episodes could be considered either a recurrent or incompletely treated infection we plan to manage these per clinical care and not based on the participants initial study arm.

Figure 2: Study Flow Diagram

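### Step 2 of the antibiotic list gives trimethoprim/sulfamethoxazole a strength of 875/125 mg, which fits that combination in neither component order, so the drug name or the dose is wrong

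*Combined protocol and SAP*

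**What the plan says.** Section D.1.1 says that women in the empiric arm "will be prescribed immediate antibiotics from an established list of commonly prescribed antibiotics". Section D.1.3.3 gives that list as five ranked items. Nitrofurantoin is first. The second item is "Trimethoprim/Sulfamethoxazole 875/125 mg PO BID x 5 days". This is the only place in the readable text where the combination or its strength appears.

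The list governs treatment at three points:

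- **Empiric arm, first prescription (D.1.3.3).** The rule is "If there is a contraindication to the first antibiotic on the list they will progress to the next option until a suitable selection is achieved". Step 2 is therefore the first alternative to nitrofurantoin.
- **Empiric arm, after a resistant culture (D.1.3.4).** "Those with a positive culture resistant to empiric antibiotic will be given an alternative antibiotic per antibiotic protocol".
- **Culture-directed arm (D.1.3.4).** Women with a positive culture and persistent symptoms "will be given antibiotics following the priority list above with consideration to reported antimicrobial sensitivities".

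On how a drug is selected in the empiric arm, D.1.3.3 adds that "we will choose an antibiotic with consideration of patient reported allergies, current medications and current IDSA guidelines". It quotes no strength from those guidelines.

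**The concern.** The line names one combination and gives a strength that does not appear to belong to it. If the two components had simply been written in the opposite order, the slip would be minor and any prescriber could undo it. If reversing them does not give a valid strength either, the fault lies in the drug name or in the numbers, and the text does not say which.

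This is a treatment instruction, and it applies in both arms. Three things depend on it:

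- **Dose.** A prescriber who reaches step 2 has no usable dose in the protocol.
- **Drug identity.** Choice in the empiric arm rests partly on allergies and current medications. Those checks need to know which drug is meant. The women are 65 or older, and section B.2 itself notes that older women are especially exposed to drug interactions.
- **Interpretation of safety data.** Section D.1.7 compares adverse events between groups and expects most of them to be antibiotic side effects. Reading that comparison requires knowing what was given and at what dose.

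**Working it through.** No sample size, power or error-rate figure is involved. The check is whether the written strength can belong to the named product.

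**Inputs from the documents (D.1.3.3, item 2)**

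- Drug: trimethoprim/sulfamethoxazole (TMP/SMX below)
- Strength: 875/125 mg
- Frequency: twice daily

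**Input assumed, not in the documents**

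- Fixed TMP:SMX ratio of 1:5, with tablets from 80/400 mg (single strength) to 160/800 mg (double strength). Both ends are carried through as a range.

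**Step 1. Component ratio**

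- As named: 875/125 = 7, so TMP:SMX is 7:1.
- Reversed (TMP 125, SMX 875): 1:7.
- Assumed product: 400/80 = 800/160 = 5, so 1:5.

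Neither order gives 1:5. At 1:5, 125 mg TMP would go with 125 × 5 = 625 mg SMX, and 875 mg SMX with 875/5 = 175 mg TMP.

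**Step 2. Can any number of tablets deliver it?** (single-strength tablets per dose)

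- As named: TMP 875/80 = 10.94 tablets; SMX 125/400 = 0.31 tablets.
- Reversed: TMP 125/80 = 1.56 tablets; SMX 875/400 = 2.19 tablets.

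In each order the two components need different tablet counts, so no single count gives both amounts. Double-strength tablets halve every count and leave the mismatch unchanged.

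**Step 3. Size of the discrepancy per day**

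Daily dose as named: TMP 875 × 2 = 1,750 mg; SMX 125 × 2 = 250 mg. Assumed reference, one tablet twice daily: 160/800 mg a day (single strength) or 320/1,600 mg a day (double strength).

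| Reading | Component | Against double strength | Against single strength |
|---|---|---|---|
| As named | TMP | 1,750/320 = 5.47 | 1,750/160 = 10.94 |
| As named | SMX | 250/1,600 = 0.16 | 250/800 = 0.31 |
| Reversed | TMP | 250/320 = 0.78 | 250/160 = 1.56 |
| Reversed | SMX | 1,750/1,600 = 1.09 | 1,750/800 = 2.19 |

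**Step 4. Does anything else in the plan settle it?** No other readable section restates the strength, gives a different one, or names another combination product. D.1.1 describes the list as antibiotics in common use, which argues against an unusual product being intended.

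**The case against.** The strongest reply has four parts.

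1. **The reference ratio comes from outside the documents.** This is true. The 7:1 and 1:7 ratios come from the plan, but calling them wrong depends on the assumed 1:5 product. That assumption is stated, with its range, and the conclusion is conditional on it.
2. **The multiples describe a dose that could not be dispensed.** This also stands. Step 2 of the working shows that no tablet count delivers the line in either order, so 5.5 to 10.9 times the trimethoprim measures inconsistency in the text and not a likely exposure.
3. **Safeguards make literal execution unlikely.** A licensed provider confirms eligibility, drug choice refers to guidelines, side effects are collected at follow-up, and a clinical line is open at all hours. A prescriber or pharmacist would probably notice the mismatch. But the guideline sentence concerns which drug is chosen and not its dose, and noticing the mismatch does not show which half of the line to follow. A slip in the strength is at least as plausible as a wrong drug name, yet two prescribers could resolve it differently and both would depart from the protocol as written.
4. **Reach is unknown.** Step 2 applies only when nitrofurantoin is unsuitable or the sensitivities point to it. The documents support no count of affected women, and none is claimed.

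One smaller limit is that the study flow diagram is not shown in the text available. If it did carry a different strength, the protocol would contradict itself, and the line would still need correcting.

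**Conclusion.** The concern holds, with high confidence. Item 2 cannot be followed as written: its component ratio is 7:1, or 1:7 if reversed, against an assumed 1:5. Swapping the order does not repair it, so the name or the strength is wrong, and the documents do not show which. The conclusion rests on one outside assumption, the 80/400 to 160/800 mg range for the standard product.

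This must be fixed because it is the dose line of a study treatment used in both arms. No harm or actual exposure has been shown. The sample size of 70, the margins of error and the primary feasibility outcome do not depend on it.

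**What to change.** The investigator should confirm which drug is intended and correct item 2 so that name, component order and strength agree with the product labelling, before any participant is prescribed step 2. I propose no dose, because the documents do not show which half of the line is right. For any woman already treated at step 2, record the product and strength actually dispensed, so that the adverse-event comparison can be read correctly.

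As a purely editorial matter in the same list, add the missing unit to the cephalexin dose and the route to items 3 and 4.

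The cost is a one-line protocol correction, with no effect on sample size, schedule or analysis.
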